Randomisation was conducted using simple randomisation, within classes (or effectively within schools where there was only one reception class). As the number of schools recruited exceeded the delivery target, as per the trial protocol, in schools with multiple reception classes, only one class was selected (at random) to complete the pre-tests. This means that while a total of 2,646 pupils were in classes eligible for testing, a total of 3,662 pupils form part of the overall trial. Pupils in the classes that were not selected for testing were still randomised; the original intention being that outcomes from the Early Years Foundation Stage Profile (EYFSP) would be analysed as secondary outcomes for the full sample of 3,662 pupils. As documented in the protocol revisions (version 1.1), analysis of EYFSP outcomes is no longer possible, as in line with other national assessments, these assessments did not take place in summer 2020 due to the Covid-19 pandemic. While beyond the scope of the current planned analysis, this larger sample could potentially be followed up in future longitudinal analysis.

Due to a small number of schools having an earlier October half-term (2019), randomisation took place in two batches, enabling parents in these schools to start receiving the texts immediately following half-term. Five schools were randomised in the first batch (20th October 2019) and the remaining 104 schools in the second batch (30th October 2019).

Sample size calculations overview

		Protocol		Randomisation	
		OVERALL	FSM	OVERALL	FSM
Minimum Detectable Effect Size (MDES)		0.10	0.14	0.10	0.15
Pre-test/ post-	level 1 (pupil)	0.4	0.4	0.4	0.4
test correlations	level 2 (class)	-	-	-	-
	level 3 (school)	-	-	-	-
Intracluster correlations	level 2 (class)	-	-	-	-
(ICCs)	level 3 (school)	0.10	0.10	0.10	0.10
Alpha		0.05	0.05	0.05	0.05
Power		0.8	0.8	0.8	8.0
One-sided or two-sided?		2	2	2	2
Average cluster size		26	10	24	9
	intervention	105	105	109	109
Number of schools*	control	105	105	109	109
30110013	total	105	105	109	109
Number of pupils	intervention	1365	525	1325	510
	control	1365	525	1321	508
	total	2730	1050	2646	1018

^{*}Note that as randomisation took place within schools (classes), all schools form part of both the intervention and control group.

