The sample size was determined with the aim of establishing a MDES of 0.1, given the previous research by York and Loeb (2018), which found an impact of the programme on literacy of 0.11 standard deviations. MDES calculations were conducted using Optimal Design software.

All estimates are based on standard EEF assumptions of 80% power and 5% significance level. We assume the pre-test explains 40 per cent of the variation in the post-test scores¹, and that 10 per cent of variance is explained by the blocking variable² (or effectively here, an ICC of 0.10). To achieve an MDES of 0.1 this suggested a required sample size of around 105 schools based on an average of 26 pupils per school (assuming an average of 30 pupils per school, and then allowing for around 5 per cent of pupils to withdraw before randomisation and around 10 per cent of the remainder lost to follow-up). As set out in the trial protocol, if it proved feasible to recruit around 105 schools (and ultimately 109 were recruited), then only 1 class per school receives the assessment that forms the primary outcome for the trial.

Department for Education Statistics for January 2019 show that 15.8 per cent of pupils in primary schools were eligible for and claiming free school meals (Department for Education, 2019). However, schools with above average proportions of pupils eligible for free school meals (FSM) were targeted in recruitment. On the assumption that on average 10 pupils within the reception year of a school will be eligible for FSM, equivalent to around 38 per cent of pupils (at the time of writing the protocol, this was the average percentage of pupils eligible for FSM in recruited schools), and keeping all other assumptions the same, this results in an MDES of 0.14. The trial is not however designed with the aim of detecting an effect for the FSM subgroup as the primary population of interest.

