At the point of randomisation, 109 schools were recruited and 2,392 pupils had completed pre-tests. In total, 2,646 pupils were in the classes selected for the pre-test, and were randomised; all of these pupils will be approached for post-test.³ This means the maximum available sample at post-test is 2,646 (note this excludes 2 pupils who were withdrawn from the study after randomisation, based on the available information at the point of preparing this SAP). Based on these numbers, and keeping all other assumptions the same as at protocol stage, this gives an MDES of 0.10. There will inevitably be some degree of attrition from the trial by the point of analysis. If we assume that ultimately 100 schools remain in the trial, with an average cluster size of 20, the MDES stands at 0.11. For the FSM subgroup, based on post-randomisation numbers, the MDES stands at 0.15. Given the likely difficulties in conducting assessments as a result of Covid-19, it is probable that attrition will be higher; with attrition of around 20 per cent of schools, this would result in an MDES of 0.12. Thus even with fairly substantial attrition, the trial would still be able to detect a relatively small effect. To help place this in context, in line with EEF guidance, an effect size of between 0.10 and 0.18 is considered to be equivalent to two months' additional progress.

_

¹ To our knowledge, there is currently no publicly available information on the likely correlation between pre- and post-test scores for our primary outcome measure, the York Assessment of Reading for Comprehension. The efficacy trial of the Nuffield Early Language Intervention (implemented with a similar age group) found that around 55% of the variation in post-test scores (a composite language score) was explained by the pre-test and pupil characteristics (Sibieta, 2016). This would be higher due to the additional inclusion of pupil characteristics; we therefore use a lower estimate of 40 per cent for our assumption.

² As noted earlier, randomisation was conducted within schools, or blocks. The sample size calculations require an estimate of the percentage of the variance explained by the "blocking variable", in this case, the percentage of the variance explained by the school (Spybrook et al., 2011). Although based on secondary schools, previous research has indicated that schools explain around 10 per cent of the variation in pupil attainment at the end of Key Stage 4 (Wilkinson et al., 2018)

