As there is just one primary outcome no adjustments for multiple comparisons will be applied.

The equation to be estimated is:

$$Y_{ijt} = \alpha + \beta_1 Treat_i + \beta_2 Y_{ijt-1} + \beta_3 \gamma_i + s_i + \varepsilon_{ij}$$

where i are pupils and j are schools, Y_{ijt} is the YARC post-test score, Y_{ijt-1} is the YARC pretest score, $Treat_i$ is our treatment indicator (a dummy variable where 1 represents being allocated to receive the intervention and 0 represents allocation to the control group, i.e. not receiving the intervention), γ_j is a dummy variable indicating randomisation batch, s_j represent school fixed effects and ε being an error term. Where pre-test scores are missing, these will be imputed using the principles set out in the missing data section. As stated above, 2,392 of the 2,646 pupils in the classes eligible for testing completed a pre-test (this can be missing, for example, where pupils were absent on the day of testing, where special educational needs meant the test wasn't suitable, and where it was not possible to return to the school to conduct

assessments in the time available⁴). All 2,646 pupils are being approached for post-testing in order to maximise the potential available sample (rather than restricting this to pupils who completed pre-tests only). Thus for some pupils with post-tests, pre-test scores will be missing.

As this is effectively a multi-site trial, school identifiers will be included as fixed effects. This is in line with the EEF Statistical Analysis Guidance for an efficacy trial.

The analysis will be conducted in Stata (version 15).

Secondary outcome analysis

The approach to the secondary outcome analysis will follow the same approach used for the primary outcome. We do not have a measure of the secondary outcome at baseline, but will include the YARC pre-test score as it is still expected that this should account for some of the variance. In all other respects the analysis will remain the same. Thus our equation to be estimated is:

$$YS_{ijt} = \alpha + \beta_1 Treat_i + \beta_2 Y_{ijt-1} + \beta_3 \gamma_j + s_j + \varepsilon_{ij}$$

where YS_{ijt} is the SDQ score, instead of the YARC post-test score (and all other elements are as defined above).

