We will assess balance by calculating absolute standardised differences (Imbens & Rubin, 2015) between the treatment and control groups and these will be presented in the report. Differences of greater than 10% will be considered as indicative of imbalance. If imbalance is observed we will run an additional sensitivity analysis incorporating any variables on which imbalance is present as additional covariates into the primary outcome model.

Missing data

We will report the number of complete cases (those without missing data). We will consider separately missingness in outcome data at post-test and missingness at pre-test, and will report the distribution of missing observations by treatment arm.

In the event of greater than 5% missing data at either cluster⁶ or individual level we will conduct further investigation into the mechanisms of missingness.

Any multiple imputation undertaken in response to missing data will focus on the primary analysis model, in line with EEF guidance. The extent to which multiple imputation is appropriate depends on the missingness mechanism.

Missing post-test data

If more than 5% of outcome data (total YARC post-test score) is missing (that is, as a percentage of the randomised sample) we will investigate the extent to which baseline characteristics (at school and pupil level)⁷ are correlated with missingness, using logistic regression, where the dependent variable is a binary indicator for missingness. If this shows significant associations with any of the characteristics, we would conduct an additional analysis including those covariates in the primary analysis model to assess the robustness of the main results.

Missing pre-test data

Again, where more than 5% of data is missing (that is, as a percentage of the randomised sample) we will undertake further investigation into the nature of missingness. This will follow the same approach outlined above of a logistic regression to explore the extent to which observed baseline characteristics are correlated with missingness.

Multiple imputation

Where the analysis above shows significant associations with the included characteristics, and where missingness does not depend on unobserved characteristics, the missing data are considered to be missing at random (MAR), and in this case, proceeding with multiple

⁶ That is, if data are missing for 5% of clusters.

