⁷ The characteristics to be included in the model will be pupil age in months, gender, FSM status and pre-test score where available, and a school identifier.

imputation (MI) is appropriate (in practical terms we will proceed with MI if any significant associations with observed characteristics are established). This MI would use those variables shown to be significant in the logistic regression alongside an indicator of treatment arm and school, using ten imputations⁸. Where appropriate, MI will be explored for imputing both pretest and post-test data. We will then compare the estimated treatment effect based on the imputed data with that from the primary analysis.

If, however, missing data depend on unobserved variables, the missing observations are missing not at random (MNAR), and this cannot be resolved through MI. In this case we would conduct further sensitivity analysis exploring the robustness of the results to differing specifications, including complete case analysis only; exclusion of the pre-test from the model, and using null imputation to impute missing pre-test scores.

Compliance

We will construct a measure of compliance based on information on whether parents opted out⁹ of receiving the texts and information on delivery of text messages. Thus compliance is effectively determined at parent level (which is applied at pupil level in the analysis – in most cases this is effectively the same, except in the case of siblings). The delivery team will provide the evaluation team with information on which parents opted out of receiving text messages and when this occurred, as well as information on whether messages were successfully delivered. This will allow the evaluation team to construct a measure of compliance, which will take a value between 0 and 1, set proportionately according to the number of messages received as a proportion of total possible messages¹⁰ (thus a value of 1 represents a parent who received all possible messages, and a value of 0.5 would represent a parent who received half of all messages).

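### The SDQ model, and the headline YARC model, omit age, gender and FSM status, which the SAP already plans to use elsewhere; the cost is a modest loss of precision, not bias

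*SAP*

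**What the plan says.** The SAP's sections on the primary and secondary outcome analyses give two equations with the same right-hand side: treatment, YARC pre-test, a randomisation-batch dummy and school fixed effects. The pre-test is therefore the only covariate that varies between pupils within a school. For the SDQ the SAP explains: "We do not have a measure of the secondary outcome at baseline, but will include the YARC pre-test score".

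The three other pupil characteristics appear elsewhere in the SAP:

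- Missing data, footnote 7, lists the predictors of missingness as "pupil age in months, gender, FSM status and pre-test score where available", with a school identifier.
- Imbalance at baseline plans to report age, gender and FSM eligibility with the pre-test score.
- Subgroup analyses takes FSM status from the NPD.

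They can reach the primary model in two ways, both conditional and both labelled as additional analyses. If a standardised difference exceeds 10%, there is a sensitivity analysis "incorporating any variables on which imbalance is present as additional covariates". If more than 5% of outcomes are missing and a characteristic is significantly associated with missingness, that characteristic is added in a robustness model. Both routes are written for the primary outcome. Subgroup analyses also confines other additional analyses to that outcome, although version 1.1 later extends the Bayesian analysis to the SDQ.

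**The concern.** When covariates are fixed in advance in a randomised comparison, adjusting for those that predict the outcome narrows the interval without biasing the treatment estimate. The SAP recognises that pupil characteristics carry such information. Footnote 1 to the sample size section cites another trial in which pre-test and characteristics together explained about 55% of the variance. It then says "This would be higher due to the additional inclusion of pupil characteristics" and takes a lower 40% for the pre-test alone.

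The YARC pre-test is also a thin sole covariate. It uses two of the four subscales, shows signs of floor effects, and is missing for 254 of the 2,646 pupils (2,646 − 2,392; 9.6%). For the SDQ it is a literacy score adjusting a behavioural outcome.

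Precision matters more since version 1.1, which reports that about a third of the anticipated post-assessments were completed. That version adds a Bayesian analysis with vague priors, which brings in almost no information, and leaves the covariate set unchanged.

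**Working it through.** **Inputs from the SAP.** "All estimates are based on standard EEF assumptions of 80% power and 5% significance level"; the table row headed "One-sided or two-sided" reads 2. "We assume the pre-test explains 40 per cent of the variation in the post-test scores", so R² = 0.40. School explains B = 0.10 of the variance. Allocation is 1:1 within class. "The sample size was determined with the aim of establishing a MDES of 0.1".

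**Assumed.** The SAP gives no post-test count. One third of 2,646 is N = 882. The anticipated number could also be read as 2,000 (100 schools of 20) or 2,730, giving 667 to 910. The SDQ count is taken to be the same. No incremental R² is given for age, gender and FSM status, so it is varied.

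**Formula (school fixed effects).** MDES = 2.80 × √[4(1 − B)(1 − R²)/N].

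**The plan's own figure.** For N = 2,646: 2.80 × √(4 × 0.90 × 0.60/2,646) = 0.080, against the stated 0.10. The listed inputs do not give 0.10 under the planned fixed-effects model. A random-effects multisite formula with an unlisted between-school effect variance of 0.05 gives 0.101. The comparison below depends mainly on the ratio of SEs, so this gap does not change its direction.

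**Primary outcome, N = 882.** The SE ratio is √[(1 − R²)/0.60].

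| R² | MDES | Power for 0.10 | SE change | Equivalent N |
|---|---|---|---|---|
| 0.40 (plan) | 0.139 | 52% | – | 882 |
| 0.41 | 0.137 | 53% | −0.8% | 897 |
| 0.42 | 0.136 | 54% | −1.7% | 912 |
| 0.45 | 0.133 | 56% | −4.3% | 962 |

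For N from 667 to 910 the MDES runs from 0.159 to 0.137 at R² 0.40, and from 0.153 to 0.131 at R² 0.45. Under the random-effects variant with 109 schools and N = 882, it goes from 0.152 to 0.147 over the same step, a slightly smaller gain.

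**SDQ, N = 882, all R² values assumed.**

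- Pre-test alone 0.05, rising to 0.08: √(0.92/0.95) = 0.984, so the SE falls 1.6%; MDES 0.175 to 0.172.
- 0.05 rising to 0.15: √(0.85/0.95) = 0.946, so the SE falls 5.4%; MDES 0.175 to 0.165; power for 0.10 rises from 36% to 40%.
- 0.02 rising to 0.15: √(0.85/0.98) = 0.931, so the SE falls 6.9%.

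**How often the imbalance trigger fires by chance.** With N = 882 the SE of a standardised difference is 2/√882 = 0.067, so P(|d| > 0.10) is about 0.138 for each variable. For three independent variables, 1 − (1 − 0.138)³ = 0.36. The pre-test is not counted because it is already in the model.

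**The case against.** A short covariate list fixed in advance is a legitimate choice, and the estimate it gives is valid. Version 1.0 predates post-testing. The shortfall appears only in version 1.1, after testing had stopped, so changing the headline model then would have been a late change. This stands, and it is why the primary model should stay as it is. It does not count against an adjusted estimate reported beside it, or against naming covariates for the SDQ.

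Four stronger readings are tempting, and the SAP does not support them:

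- **That the characteristics are worth 15 points of R².** The 55% belongs to another trial and a composite language score. The 40% is the authors' cautious guess for YARC, not that trial's pre-test-only figure. The gap is not an increment due to age, gender and FSM status, and the pre-test and school effects may already absorb part of their signal. R² of 0.55 would give an MDES of 0.120 and 65% power, but this is a generous bound, not a forecast.
- **That the main result depends on chance imbalance.** The headline covariate set is fixed. Only additional models depend on the triggers.
- **That the data are already held and complete.** FSM status is to come from the NPD. The SAP does not say that linkage is done, or that age and gender are complete.
- **That the omission biases the estimate.** It does not.

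**Conclusion.** The point holds as a modest loss of efficiency. It is clearest for the SDQ, which has no baseline measure of its own, one pupil-level covariate from a different domain, and no adjusted analysis under any condition. For the primary outcome, whether an adjusted estimate is reported depends on triggers that select on chance imbalance or on association with missingness, not on prognosis.

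The size rests on assumed R² increments and about 880 post-tests. The primary SE falls by about 1-4%, equal to roughly 15 to 80 extra pupils, and the SDQ SE by about 2-7%. Floor effects could put the real pre-test R² below 0.40, in which case the starting MDES is worse than shown. In no case examined is the 0.10 target recovered, so the covariates do not repair the loss of sample.

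**What to change.** - **SDQ:** name age in months, gender and FSM status as covariates in the total difficulties model, with no trigger.
- **YARC:** keep the existing model as the headline. Beside it, always report a pre-specified estimate adjusted for the same three variables, whether or not an imbalance or missingness condition is met.
- **Missing characteristics:** use a missing-indicator category for absent values, so that no pupil is dropped for lack of one. The SAP's existing rules for a missing pre-test are unaffected.
- **Timing:** fix the set before outcomes by arm are seen, and record the date. If they have already been seen, label the adjusted estimates as post hoc.
- **Subgroups:** if the set is carried into the separate FSM and non-FSM models, FSM status drops out there because it is constant.

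The cost is SAP wording and one extra reported YARC model, with no new data collection beyond what the SAP already plans. The adjusted estimates will depend on the planned NPD linkage for FSM status, so its completeness should be reported by arm.
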